#### **Retention of Records**

Records and documents pertaining to the conduct of this study at the MAH must be retained for at least 15 years after completion of the study, or for the length of time required by relevant national or local health authorities, whichever is longer. After that period of time, the documents may be destroyed, subject to local regulations.

#### 8.9 LIMITATIONS OF RESEARCH METHODS

Participating centers report to EUHASS information on adverse events and aggregate data on the number of patients receiving each hemostatic drug. Although EUHASS follows up and confirms the accuracy of each adverse event reported, no systematic site audit is performed to confirm the accuracy and completeness of the information recorded.

Centers provide information on the number of patients who receive, during the same calendar year, emicizumab alone and with each of the following drugs: aPCC, rFVIIa, and FVIII. This information is used to calculate, as part of the secondary objective, the annual incidence of TE and TMA among patients who receive emicizumab and one of these drugs. However, it is not possible to know with certainty if the co-administration of the drugs was sequential (patients switched from a different drug to emicizumab) or concomitant (e.g., patients treated with emicizumab prophylaxis received another drug to treat a breakthrough bleed or peri-operatively). The proposed analysis assumes that the administration is concomitant, and therefore it is the most conservative approach as it may overestimate the annual incidence of TE and TMA in patients receiving emicizumab with a coagulation factor product and may underestimate the annual incidence of TE and TME in patients receiving emicizumab alone.

EUHASS is set up as a pharmacovigilance reporting system, rather than a research study, and patient informed consent is only obtained in selected centers where this is

required by the local Ethics Committee. Therefore, in the case of adverse event reporting, EUHASS does not have the ability to systematically collect additional and follow-up information that may be valuable to understand the context in which the adverse event occurred and the outcomes of these events.

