# RATIONALE AND BACKGROUND

Emicizumab (also known as Hemlibra®, ACE910, and RO5534262) is a humanized monoclonal modified immunoglobulin G4 (IgG4) antibody being developed for the treatment of patients with hemophilia A.

Emicizumab was first granted marketing approval in the United States (US) on 16 November 2017. Subsequently, it was first approved in the European Union (EU) on 23 February 2018 and in Japan on 23 March 2018 for patients with congenital hemophilia A with FVIII inhibitors. Over 25,000 patients have received emicizumab through clinical trials and post-authorisation to date.

As of October 2023, emicizumab is approved in approximately 119 countries worldwide in patients with hemophilia A with FVIII inhibitors and is approved in approximately 107 countries worldwide for the expanded indication to include patients with hemophilia A without FVIII inhibitors, including approval in the US, Japan, and the EU.

Two important risks have been identified with the concomitant use of activated prothrombin complex concentrate (aPCC) in patients treated with emicizumab prophylaxis: thromboembolic events (TE) and thrombotic microangiopathy (TMA). In addition, anaphylaxis, anaphylactoid, or systemic hypersensitivity reactions were considered as potential safety risks based on the class of biological drugs.

In order to better assess the incidence of TE, TMA, and anaphylaxis, the Sponsor will use information collected by the European Haemophilia Safety Surveillance (EUHASS) pharmacovigilance program. EUHASS will provide the Sponsor with an emicizumab-specific annual report, the findings of which will be used to calculate the incidence of the TE, TMA, and anaphylaxis in the real-world setting.

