#### 7.2 OBJECTIVES

The primary objective for this study is as follows:

 To estimate the incidence of TE, TMA, and anaphylaxis in patients exposed to emicizumab, with or without coagulation factor products

The secondary objectives for this study are as follows:

- To estimate the incidence of TE and TMA in patients exposed to emicizumab alone and concomitantly with each of the following drugs: aPCC, rFVIIa, and FVIII product
- To describe individual cases of TE and TMA based on available information
- To summarize the frequency of other adverse events collected by EUHASS in patients exposed to emicizumab
- To describe individual cases of "unexpected poor efficacy" reported to EUHASS based on the available information

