# 8. RESEARCH METHODS

# 8.1 STUDY DESIGN

This is a cohort surveillance study based on data provided in the EUHASS emicizumab-specific annual report.

EUHASS is a pharmacovigilance program dedicated to monitoring the safety of treatments in people with inherited bleeding disorders across Europe. Participating centers provide information on patients who experience certain adverse events, including but not limited to thrombosis and allergic and other acute reactions. Other adverse events collected are: transfusion transmitted infections, new inhibitors, new malignancy, death, unexpected poor efficacy, and other adverse events possibly related to concentrate. For each type of adverse event, the subtype is specified according to a pre-specified list (e.g., TMA will be collected under the 'thrombosis' category, while anaphylaxis is collected under 'allergic and other acute reactions' category). For all patients who experience reported adverse events, centers are asked to collect selected demographic and disease-related information (i.e., age, gender, diagnosis, factor level, event date). Additionally, specific information is requested for each type of adverse event. This information includes:

- In the case of a thrombotic event: nature of thrombotic event, concentrate administered in the 30 days prior to the event (Y/N), prophylactic treatment (Y/N), time from last dose and event onset, all the concentrate products infused in the last 3 months prior to event, additional blood products used (blood, fresh frozen plasma [FFP], cryoprecipitate) thrombosis associated with central venous catheter (Y/N) and catheter type, surgery in the last 3 months (Y/N), type of surgery, thromboprophylaxis treatment associated with surgery (Y/N), risk factors for thrombosis.
- In the case of allergic or other acute reactions: type of acute event (including anaphylaxis), product infused, other blood products, time from infusion to event onset, lifetime exposure days, history of the same event, outcome, relationship between concentrate and event (in physician's opinion).

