Participating centers are asked to provide information on the adverse events quarterly by completing a Web-based adverse event reporting form and have the option of reporting an event at the time of its occurrence. Annually, centers also provide information on the number of patients treated with each type of coagulation product, allowing for calculation of annual incidence rates of each adverse event collected across the entire registry by product. In addition, EUHASS will also collect aggregate information on the number of patients who use emicizumab and aPCC, emicizumab and rFVIIa, and emicizumab and FVIII, thus allowing for calculation of incidence rates of TE and TMA among patients exposed to emicizumab concomitantly with each of these drugs.

Based on information collected from the participating centers, **EUHASS generates emicizumab-specific annual reports** indicating the number of patients who receive

emicizumab, listings of patients exposed to emicizumab who develop each type of adverse event, as well as limited additional information related to the occurrence of each adverse event, as described above for thrombotic events and allergic or other acute reactions. Based on these, the **Marketing Authorization Holder generates annual PASS reports**, presenting the following:

- Number of patients exposed to emicizumab (directly from EUHASS report)
- Number of patients exposed to emicizumab who experienced TE, TMA, and anaphylaxis (directly from EUHASS report)
- Proportion of each adverse event among patients receiving emicizumab (calculated based on information from EUHASS report if relevant)
- Number of patients exposed to emicizumab and each of the following drugs: aPCC, rFVIIa, FVIII (directly from EUHASS report)
- Number of patients exposed to emicizumab and each of the following drugs: aPCC, rFVIIa, FVIII, who experienced TE and TMA (directly from EUHASS report)
- Proportion of TE and of TMA among patients exposed to emicizumab and each of the following drugs: aPCC, rFVIIa, and FVIII (calculated based on information from EUHASS report if relevant)

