# 8.3.2 Secondary Variables

The secondary variables for this study are as follows:

- Transfusion transmitted infections
- New inhibitors (antibodies against the coagulation factor)
- Allergic and other acute reactions, with the exception of anaphylaxis
- New malignancy diagnosis
- Death

- Unexpected poor efficacy
- Other adverse events possibly related to concentrate
- Exposure to emicizumab, without replacement factor products in the same calendar year
- Exposure to both aPCC and emicizumab in the same calendar year
- Exposure to both rFVIIa and emicizumab in the same calendar year
- Exposure to both FVIII and emicizumab in the same calendar year

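### Section 8.9 calls counting every same-year pairing as concomitant the most conservative choice, but sequential switchers in the denominator can bias the combination proportions downward

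*Protocol*

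**What the plan says.** The secondary objective in Protocol section 7.2 is the incidence of TE and TMA "in patients exposed to emicizumab alone and concomitantly with each of the following drugs": aPCC, rFVIIa and FVIII. The variable that stands for joint use in section 8.3.2 is wider, for example "Exposure to both aPCC and emicizumab in the same calendar year". The estimator in section 8.1 is the "Proportion of TE and of TMA among patients exposed to emicizumab and each of the following drugs: aPCC, rFVIIa, and FVIII".

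Section 8.9 discloses that "it is not possible to know with certainty if the co-administration of the drugs was sequential" or concomitant. It then assumes concomitant use throughout and defends this on the ground that "it is the most conservative approach as it may overestimate the annual incidence of TE and TMA" in the combination groups. It adds that the incidence for emicizumab alone may be underestimated.

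The synopsis (Rationale and Background) gives the expected direction of risk: "Two important risks have been identified with the concomitant use of activated prothrombin complex concentrate (aPCC) in patients treated with emicizumab prophylaxis". Section 6 says much the same.

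**The concern.** The defence in section 8.9 follows events only. An event that fell before or after the period of overlap may be credited to the combination, and that raises the numerator. The same rule also places every sequential switcher in the denominator, although these patients never had joint exposure. The protocol does not mention this second effect. If joint exposure carries the excess risk, the switchers pull the proportion down.

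For a safety estimate, a bias that shrinks a possible interaction is not conservative. A reader who accepts the claim could take a low combination proportion as an upper limit on the risk of joint use. The results go to EMA each year through the PSUR/PBRER (sections 8.7.1 and 11), so the stated direction of bias affects how they are understood.

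**Working it through.** Section 8.9 gives a direction and no figure, so the check is on the direction.

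**Inputs from the protocol.** Combination exposure is any use of both agents in one calendar year (8.3.2). The proportion is taken among all such patients (8.1). The 2021 counts (8.5) are 1,319 on emicizumab alone, 490 with FVIII, 71 with rFVIIa and 3 with aPCC.

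**Assumptions.** The documents give neither the concomitant share f nor the risks p1 (concomitant users) and p0 (switchers). They are varied below.

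**Formula.** p_obs = f·p1 + (1−f)·p0, so the bias is p_obs − p1 = −(1−f)·(p1 − p0). It is negative if p1 > p0, zero if they are equal and positive if p0 > p1.

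**Downward case, p1 = 1%, p0 = 0.1%.**

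| f | p_obs | Shortfall against p1 |
|---|---|---|
| 75% | 0.75×1% + 0.25×0.1% = 0.775% | 22.5% |
| 50% | 0.50×1% + 0.50×0.1% = 0.55% | 45% |
| 25% | 0.25×1% + 0.75×0.1% = 0.325% | 67.5% |

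**Other risk ratios.** With R = p1/p0 the relative shortfall is (1−f)·(1−1/R). For f = 75%, 50%, 25% it is 20%, 40%, 60% at R = 5; 12.5%, 25%, 37.5% at R = 2; and nil at R = 1.

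**Upward case.** With p1 = 2%, p0 = 4% and f = 50%, p_obs = 0.5×2% + 0.5×4% = 3%. Overestimation therefore needs switchers to be at higher risk than concomitant users, for example through events on the earlier product before the switch.

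**Upper confidence limit.** Take a group of 490 (the size of the 2021 FVIII group) with assumed p1 = 2.0% and p0 = 0.2%. The chance that the exact 95% upper limit of the pooled proportion still reaches 2.0% is 79% at f = 50%, 39% at f = 25% and 12% at f = 10%. This shows the mechanism at that group size; the protocol states no excess risk with FVIII.

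**Emicizumab alone.** Suppose half of the 490 are switchers (245, assumed) and carry the alone risk of 0.2% (assumed). Returning them to the alone group gives (1,319×0.2% + 245×0.2%) / (1,319 + 245) = 0.2%. Nothing changes, so the stated underestimate does not follow in that case.

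**aPCC.** With no events in 3 patients the exact 95% upper limit is 1 − 0.025^(1/3) = 70.8%. Dilution is immaterial beside that.

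**Timing cases only.** If the numerator were limited to truly concomitant cases and the denominator left as it is, the result would be f·p1 = 0.75%, 0.50% and 0.25% for f = 75%, 50% and 25%. That is 25%, 50% and 75% too low, worse than the table above. Dividing by f·N instead returns f·p1·N/(f·N) = p1.

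**The case against.** Section 8.9 discloses the misclassification and hedges twice with the word may. Overestimation is possible. The estimates are secondary and descriptive, no threshold or formal comparison is planned, and section 8.7 makes the proportions optional. Individual TE and TMA cases will be described, so timing may be visible case by case. The assumed risks come from outside the documents, and the only interaction the protocol names, aPCC, had 3 patients in 2021. All of this stands, and it limits the weight of the point. It does not rescue the claim: hedging the size of a bias does not justify calling the approach the most conservative one when its direction is open, and is downward under the protocol's own premise.

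A reader might infer more than the documents support in three ways.

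- *That the study's main question is compromised.* It is not. The primary objective in section 7.2 is overall incidence with or without factor products, and sorting patients among combination groups does not touch it.
- *That the bias is certainly downward, or largest for FVIII.* It is downward only if p1 > p0. The protocol states no excess risk with FVIII and gives no switching rates by agent.
- *That the event form already allows cases to be classified and so cures the problem.* The 30-day item in section 8.1 is a yes/no for any concentrate. Only the 3-month item lists products ("all the concentrate products infused in the last 3 months prior to event"), and the text at hand does not show whether emicizumab, an antibody, is entered there. No such timing is described for the denominator. Section 8.1 takes the combination event counts from the EUHASS report without saying how a case is assigned, but under either assignment rule the denominator still holds the switchers.

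**Conclusion.** The justification in section 8.9 is wrong as written. The same-year rule can bias a combination proportion in either direction. It biases it downward by (1−f)·(p1 − p0) whenever concomitant use carries the higher risk, as the protocol expects for aPCC. In the illustration (assumed 1% against 0.1%) the proportion is 22.5% to 67.5% too low for concomitant shares of 75% down to 25%; with smaller risk ratios the shortfall is smaller, and with none it vanishes. The companion statement about emicizumab alone does not follow if switchers carry the alone risk.

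The error is confined to how the secondary combination estimates are described and read. For aPCC, imprecision at the 2021 count outweighs it; in larger groups dilution would matter more, if an excess risk exists there. It deserves correction because it changes what may be concluded from those proportions, but it is not a defect of the primary analysis.

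**What to change.** 1. **Section 8.9.** Delete the claim that the approach is the most conservative. State that the bias can run either way, that it runs toward missing an interaction if concomitant use carries excess risk, and that a combination proportion must not be read as an upper bound. Make the remark on emicizumab alone conditional on the switchers' risk.
2. **Section 8.7.** Report each combination proportion with a sensitivity table over a stated range of f, for example p1 = (p_obs − (1−f)·p0)/f with a stated p0. Check: p_obs = 0.55%, f = 50% and p0 = 0.1% return (0.55% − 0.05%)/0.5 = 1%. Label f and p0 as assumptions and the table as a sensitivity range, not a bound.
3. **Sections 8.1 and 8.7, conditional.** Confirm with EUHASS whether the 3-month product field captures emicizumab. If it does, show the number of cases with both agents in the look-back beside the calendar-year number. Do not divide that count by the unadjusted same-year denominator, which deepens the dilution; divide it by f·N over the same range of f. A 3-month window may still not separate a recent switch from joint use, and the report should say so.

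The cost is a few sentences, one question to EUHASS and a small extra table in each annual report. No new data collection is needed for items 1 and 2.

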# 9. PROTECTION OF HUMAN PATIENTS

#### 9.1 INFORMED CONSENT

Each individual center participating in the EUHASS Registry determines if patient informed consent is required, according to the local Ethics Committee opinion. A generic patient information sheet and consent form provided by EUHASS are in Appendix 1 (see Appendix 4 of the EUHASS Working Protocol).

Centers may not submit event data to EUHASS until the opinion of their local ethics or institutional review board is known and its approval obtained, if required.

Information on patients who experience adverse events is reported anonymously on the EUHASS website, using a coding system derived by the reporting center. It is not possible to identify the patient from the details transmitted to the EUHASS project.

#### 9.2 COMPLIANCE WITH LAWS AND REGULATIONS

This study will be conducted in full conformance with the Guidelines for Good Pharmacoepidemiological Practice (GPP) published by the International Society of Pharmacoepidemiology (ISPE) and the laws and regulations of the country in which the research is conducted.

The study will comply with national and European Union requirements for ensuring the well-being and rights of participants in non-interventional post-authorization safety study (NI-PASS).

#### 9.3 INSTITUTIONAL REVIEW BOARD OR ETHICS COMMITTEE

Participating centers must find out if a formal application for approval to submit data to EUHASS is required. Each center must notify the Steering Committee of the outcome of their enquiry and progress with obtaining approval is recorded via SharePoint on the EUHASS website. The decision on whether patient consent is sought is the responsibility of individual centers and depends on their ethics committee's opinion.

Centers may not submit events data to EUHASS until the opinion of their local ethics committee or institutional review board is known and its approval obtained, if required.

# 10. MANAGEMENT AND REPORTING OF ADVERSE EVENTS/ADVERSE REACTIONS

This is a NI-PASS involving the use of secondary data. As per the EMA Guideline on Good Pharmacovigilance Practices (GVP), Module VI–Management and reporting of

adverse reactions to medicinal products, the reporting of adverse reactions in the form of individual case safety reports (ICSRs) is not required (GVP VI.C.1.2.1.b). Information received from EUHASS on all the pre-specified adverse events will be included in the study interim and final reports.

It is assumed that safety reporting of data that are going to be extracted/analyzed as part of this study have been appropriately performed and documented at the time these data are collected through primary data collection mechanism.

Adverse events collected in EUHASS are not collected according to MedDRA classification. Most events are collected according to pre-specified lists; however, free-text fields are also available for each event. To the possible extent, adverse events will be coded by Roche according to MedDRA PT level using the most current MedDRA version.

All adverse events extracted from the data source for the study as specified in the protocol will be summarized as part of any interim safety analyses and in the final study report and final publication. A listing of the events reported by EUHASS with the corresponding MedDRA attribution assigned will be provided.

As per protocol, these aggregate summaries may include the following adverse event types:

- Serious adverse events, including all deaths
- Non-serious adverse events
- Reports of lack of efficacy
- Drug interactions

# 10.1 ADVERSE EVENTS

According to the International Conference of Harmonisation (ICH), an adverse event is any untoward medical occurrence in a patient or clinical investigation subject administered a pharmaceutical product, regardless of causal attribution. An adverse event can therefore be any of the following:

- Any unfavorable and unintended sign (including an abnormal laboratory finding), symptom, or disease temporally associated with the use of a medicinal product, whether or not considered related to the medicinal product
- Any new disease or exacerbation of an existing disease (a worsening in the character, frequency, or severity of a known condition)
- Recurrence of an intermittent medical condition (e.g., headache) not present at baseline
- Any deterioration in a laboratory value or other clinical test (e.g., electrocardiogram [ECG], X-ray) that is associated with symptoms or leads to a change in study treatment or concomitant treatment or discontinuation from study medicine.

#### 10.2 SERIOUS ADVERSE EVENTS

A serious adverse event is any adverse event that meets any of the following criteria:

- Is fatal (i.e., the adverse event actually causes or leads to death)
- Is life-threatening (NOTE: The term "life-threatening" refers to an event in which the patient was at immediate risk of death at the time of the event; it does not refer to an event that hypothetically might have caused death if it were more severe.)
- Requires or prolongs inpatient hospitalization
- Results in persistent or significant disability/incapacity (i.e., the adverse event results in substantial disruption of the patient's ability to conduct normal life functions)
- Is a congenital anomaly/birth defect in a neonate/infant born to a mother exposed to study medicine
- Is a significant medical event in the physician's judgment (e.g., may jeopardize the patient or may require medical/surgical intervention to prevent one of the outcomes listed above)

[figure not shown]
The terms "severe" and "serious" are not synonymous. Severity refers to the intensity of an adverse event (e.g., rated as mild, moderate, or severe, or according to NCI CTCAE criteria; the event itself may be of relatively minor medical significance (such as severe headache without any further findings).

[figure not shown]
